## 8.5 Interim Analyses and Data Monitoring

No formal interim analyses were planned nor carried out for this study. The study was overseen by a Data and Safety Monitoring Board (DSMB) that reviewed the pooled and by-treatment subject disposition, study conduct and safety data approximately every 6 months.

## 8.6 Multiple Testing

Statistical testing is conducted at the 0.05 significance level using two-tailed tests; two-sided p-values are reported. No adjustments for multiplicity were planned since there is one primary analysis of the primary endpoint at the end of the study. Secondary analyses of the primary endpoint and analyses of the secondary endpoints serve to assess the robustness of the results and consistency of treatment effect on clinical outcomes important in this disease.

# 9 Summary of Study Conduct Data

Descriptive summary statistics are tabulated for baseline patient demographics and clinical characteristics, separately by treatment group and overall. Intervention groups are characterized as “MMF+PFD” and “MMF+Plac”. For pooled summaries, “Overall” is used as the column heading. All tables are annotated with the total population size relevant to that table, including any missing observations.

Continuous variables are summarized using descriptive statistics including n, mean, median, standard deviation, range (e.g., minimum and maximum) and using boxplots to examine the distributions of baseline characteristics by treatment group. Qualitative variables are summarized using counts and percentages. Unless otherwise specified, statistical analyses are performed using SAS Version 9 or higher.

## 9.1 Subject Disposition

Participant disposition is summarized descriptively. The number and percentage of participants randomized, completed, and withdrawing, along with reasons for withdrawal, are tabulated and summarized in a CONSORT diagram overall, and by treatment group. The number of participants in each analysis population are reported. Other disposition and study conduct information, including major protocol violations are summarized. Duration of the study follow-up is summarized overall and by treatment group.

## 9.2 Protocol Deviation

A protocol deviation is any noncompliance with the clinical trial protocol, GCP, or MOP requirements. The noncompliance may be either on the part of the participant, the investigator, or the study site staff. Protocol deviations were classified as major or not major by the study team; major protocol deviations are incorporated into the definition of the Per Protocol Analysis Set. Protocol deviations are summarized overall and by treatment group. Major protocol deviations are provided in a listing by treatment group.

### 9.3 Demographic and Baseline Variables

Demographic and baseline variables for participants include: age in years at consent, dichotomized age (18-35 years, >35-55 years, >55-75 years, >75 years), sex (Male/Female), ethnicity (Hispanic or Latino/not Hispanic or Latino), race (White/Black or African American/Asian/American Indian or Alaskan native/native Hawaiian or other Pacific Islander), % predicted FVC, FVC (ml), % predicted DLCO (corrected for hemoglobin), time from first non-Raynaud manifestation of SSc in months at screening, modified Rodnan Skin Score (mRSS), Scleroderma classification, Mahler Baseline Dyspnea Index (BDI), St. George's Respiratory Questionnaire (SGRQ) – total and each domain score, Scleroderma Scleroderma Health Assessment Questionnaire (SHAQ), including HAD-DI without Aids/Devices and SHAQ-DI VAS domains, Leicester Cough Questionnaire (LCQ) – total and three supplemental questions, PROMIS-29 domains, UCLA SCTC GIT, physician global assessment, patient global assessment, height, weight, HRCT at screening – quantitative lung fibrosis score in the whole lung (QLF-LM), quantitative lung fibrosis score in the lobe of maximal involvement (QLF-WL), quantitative interstitial lung disease score in the whole lung (QILD-LM), quantitative interstitial lung disease score in the lobe of maximal involvement (QILD-WL), and total lung capacity at maximum inspiration (HRCT-TLC), and laboratory data at screening – sodium, potassium, chloride, CO2, BUN, creatinine, glucose, protein, albumin, bilirubin, alkaline phosphate, AST, ALT, cholesterol, WBC, hemoglobin, hematocrit, platelets, neutrophil percent, absolute neutrophil count, lymphocyte percent, absolute lymphocyte count.

### 9.4 Treatment Compliance

Compliance with study medication (MMF and PFD/Plac) is assessed and summarized, including

- the proportion of participants who adhered to study treatment, overall and at each study visit,
- the median duration of adherence to study treatment (defined in section 11.1),
- the proportion of participants reaching maximum dose,
- the proportion of participants who sustain their maximum dose,
- the time to reach the maximum dose, and
- the time remaining at the maximum dose.

These are calculated and summarized overall and by treatment group. The maximum dose is 12 pills/day for MMF (1500 mg) and 9 pills/day for PFD (801 mg)/Plac. The proportion of the maximum dose that the participants reached during study period is summarized overall and by treatment group. Participants were expected to take study medication unless it was permanently discontinued due to an AE. The study medication log (Form 027), adverse event form (Form 044), serious adverse event form (Form 045) and final status form (Form 035) are used to derive the compliance measure.

The proportion of participants who permanently discontinued study medication will be summarized with descriptive statistics, overall and by treatment group. A Kaplan-Meier curve will present the time to permanent discontinuation of study medication by treatment group. A listing of these participants with their reason for permanent discontinuation of study medication will be provided.

## 10 Efficacy Analyses

Continuous variables will be summarized using descriptive statistics including n, mean, median, standard deviation, and range (e.g., minimum and maximum). Qualitative variables will be summarized using counts and percentages. Summaries will be provided by treatment groups and overall.

## 10.1 Primary Efficacy Analysis

The primary endpoint is change from baseline in the mean forced vital capacity, measured as the percentage of the age-, height-, gender- and race-adjusted predicted value (FVC-%) over the course of the 18-month treatment period, as reported quarterly (i.e., months 3, 6, 9, 12, 15 and 18). The primary efficacy analysis tests the null hypothesis that the differences between the MMF+PFD and MMF+Plac is zero. The primary analysis of the primary efficacy endpoint uses the m-ITT analysis set. The endpoint is analyzed using a linear mixed model with participant-month in the study (3, 6, 9, 12, 15, 18) as the unit of analysis and the change from baseline in FVC-% as the outcome, with terms for baseline FVC-%, treatment group, month, the interaction of month and treatment group, and prior MMF therapy (stratification factor: naïve, >0 to  $\leq$ 3 months, and >3 months to 6 months), as fixed covariates. Study participant is treated as a random effect to account for the correlation of outcomes over time within a participant.

The model is summarized below.

$$FVC\%-_{it} = \mu_0 + \mu_1 \text{TRT}_i + \mu_2 \text{MONTH}_{it} + \mu_3 \text{TRT}_i \times \text{MONTH}_{it} + \mathbf{x}_i' \boldsymbol{\beta} + \epsilon_{it},$$

where  $FVC\%-_{it}$  is the change of FVC-% from baseline at time  $t$  for patient  $i$  (that is, FVC-% at time  $t$  - FVC-% at baseline),  $i = 1, \dots, 51$ ;  $t = 1, \dots, 6$  (corresponding to 3, 6, 9, 12, 15 and 18 months).  $\text{TRT}_i$  is treatment group (equal to 1 for the PFD and MMF and 0 for Plac and MMF) for patient  $i$ .  $\text{MONTH}_{it}$  is the study month at time  $t$  for patient  $i$ . Two dummy variables for prior MMF therapy (stratification factor: naïve, >0 to  $\leq$ 3 months, and >3 months to 6 months), and baseline FVC-% for subject  $i$  are included in a vector  $\mathbf{x}_i$  of 3 covariates ( $x_1, x_2, x_3$ ) and associated fixed effects are stored in vector  $\boldsymbol{\beta} = (\beta_1, \beta_2, \beta_3)$ . We assume that residual errors  $\epsilon_{it}$  ( $t = 1, \dots, 6$ ) for subject  $i$  are normally distributed with zero mean and 6x6 general/unstructured variance-covariance matrix.

In the context of the primary analysis of the primary endpoint, we are interested in parameter  $\mu_3$ , representing the trajectories of the primary endpoint adjusted for stratifying variables and baseline covariates.

The model generates adjusted estimates of change from baseline in the FVC-% for each treatment group and month, and an F-test is used to test the hypothesis that the mean change from baseline during the treatment period differs between the two treatment groups.

The model-based adjusted mean change from baseline in FVC-% will be presented graphically by treatment group by study month, with 95% confidence intervals (CIs) provided at each month.

Analysis	Primary Analysis of the Primary Endpoint: mean FVC-% change from baseline during the treatment period differs between the two treatment groups
Analysis Set	mITT Population
Methods	Linear mixed model for repeated measures with correlated errors
Dependent Variable	Change of FVC-% measured at 3, 6, 9, 12, 15 and 18 months (FVC-% at x months – FVC-% at baseline, where x=3, 6, 9, 12, 15 and 18)
Model	Fixed effects: 
 
• Treatment
 
• Study month
 
• Interaction of treatment and study month
 

	
 
• Stratifying variable: prior MMF therapy with 3 categories
 
• Baseline FVC-%
 

Results	
 
• Estimates of mean change from baseline in FVC-% during the treatment period (slope) by treatment group and treatment difference
 
• 95% confidence interval for treatment estimates and treatment difference
 
• P-value for treatment difference
 

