5 STUDY ENROLLMENT AND WITHDRAWAL

5.1 PARTICIPANT INCLUSION CRITERIA

In order to be eligible for randomization as a study patient, an individual must meet all of the following inclusion criteria. Notes are included, as needed, to provide additional explanation and/or background rationale for selected criteria (see bullet points). Patients will provide consent prior to the screening and screening is included as part of the consent process. Note that the screening occurs in stages in order to limit unnecessary testing:

Screening criteria that must be met prior to moving forward to HRCT imaging

- 5.1.1 Age ≥ 18 yrs
- 5.1.2 Scleroderma as determined by the 2013 ACR/EULAR classification criteria.
- 5.1.3 Grade ≥ 2 on the Magnitude of Task component of the Mahler Modified Dyspnea Index (Becomes short of breath with moderate or average tasks such as walking up a gradual hill, climbing less than three flights of stairs, or carrying a light load on the level).
- 5.1.4 FVC-% of $\leq 85\%$ at screening.
 - NOTE: Inter-test variability for FVC-% can range up to 10% and therefore some participants with an FVC-% between 80-85% at screening might exceed an FVC-% of 85% when testing is repeated at the baseline.
 - NOTE: The acceptable reproducibility of the FVC-% at baseline will be governed by inclusion criteria #7 detailed in Section 5.1.7 below.
- 5.1.5 Onset of the first non-Raynaud manifestation of SSc within the prior 84 months.
 - This criteria is based on the natural history SSc-ILD which is known to be more progressive early after the onset of scleroderma and become less active over time.

Screening HRCT imaging

- 5.1.6 Presence of any ground glass opacification (any GGO) on thoracic HRCT
 - This criteria defines a population with active and measurable parenchymal lung involvement.

Final screening criteria fulfilled at Baseline Visit, but prior to randomization

- 5.1.7 Repeat FVC-% at the baseline visit within 10% of the FVC-% value measured at screening. If

these criteria are not met, a repeat FVC-% may be obtained within 7 days and the subject may qualify for randomization if the repeat FVC-% agrees within 10% of the FVC-% obtained at screening.

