7.1.1 Study Specific Procedures

7.1.1.1 **Spirometry**. Spirometry will be performed under the direction of the pulmonology investigator at each site and carried out by either certified pulmonary function technologists (National Board of Respiratory Care) or experienced staff that meet American Thoracic Society (ATS) recommendations (15). All spirometry equipment and procedures will conform to the most recently published standards of the American Thoracic Society (ATS)/European Respiratory Society (ERS) Task Force (34,41). Forced expiratory maneuvers will be performed at least in triplicate with the minimal requirement that three maneuvers are "acceptable" and that two of these maneuvers meet end-of-test and repeatability criteria for FVC and Forced Expiratory Volume in the first second (FEV1). Printouts of all data and curves will be sent to the Pulmonary Function Core at UCLA for central quality control monitoring with individual optimization and re-training for study specific requirements at each site if required to assure standardized and reproducible measurements. Spirometry results will be expressed both as measured values and as a percentage of gender-specific predicted values using the regression equations of Hankinson (17) for spirometry. For spirometry, the race-specific regression equations of Hankinson (17) will be used for African-Americans and Mexican-Americans and normal referenced values multiplied by 0.88 for Asians (17a). Spirometry measurements will be performed at entry (screening), just prior to initiation of study medication (baseline) and every 3 months for the entire 18 months of the study.

In the event that a participant has already completed spirometry testing within 30 days of Screening Visit #1 and the testing meets all eligibility criteria, it may be used in lieu of repeating the spirometry measurements at Screening Visit #1. In order to be considered eligible, the testing must have been performed at the same facility that will be used during the study, the full spirometry data set must be available for review and it must pass a Quality Assurance review by the Pulmonary Function Core at UCLA.

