7.2.1 Screening Visits (Study Day -90 through 0; Screening Visit #1&2)

In order to be eligible for randomization, patients must proceed through a series of screening steps. At Screening Visit #1, a preliminary evaluation is performed and if eligibility criteria are met the patient will proceed to the screening HRCT scan (Screening Visit #2) to assess for the presence of any ground glass opacity and to exclude concurrent findings of concern that may require additional evaluation or exclude the patient from further participation. If all inclusion and exclusion criteria are met, the patient will proceed to the baseline evaluation where a final check of pulmonary function and pregnancy testing is required to meet randomization criteria:

7.2.1.1 **Screening Visit #1.** (preferably within 60 d, but no earlier than 90 d prior to randomization)

- Patient provides written informed consent and research HIPAA authorization prior to any evaluation or testing.

- b. A review of existing medical records and tests, provided by the patient or referring physician, is performed to document the history of scleroderma and general medical history.
- c. Vital signs obtained.
- d. The patient undergoes a complete medical history and physical examination.
- e. Review of concomitant medications including all medications taken within past 3 months and any prior use of medications detailed in Section 7.5.1 (Prohibited Medications & Treatments with Potential Disease Modifying Effects).
- f. Pulmonary function testing for spirometry and diffusing capacity will be completed unless acceptable testing has been completed within 30 days of the screening visit and approved in advance by the Pulmonary Function Core at UCLA.
- g. A limited subset of the UCLA SCTC GIT questionnaire (including only Questions #1-8) is completed by the participant
- h. The patient has blood drawn for monitoring blood tests and serum pregnancy test (if applicable).

7.2.1.2 **Screening Visit #2.** (may not be completed until results from screening visit #1 confirm potential eligibility, must be completed within 60 days of randomization)

- a) Thoracic HRCT with visual review for the presence of entry and exclusion criteria and with Quantitative Image Analysis

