10.5.2 Assumptions

Based on these available data, the following assumptions were used to generate clinical outcome scenarios for the potential response of FVC-% over time for both the control arm (MMF+Plac) and the experimental arm (MMF+PFD) of SLS III:

- 1) Data from SLS I and II were used as the best available data to estimate the standard deviation of the FVC-% values at different times in the study and the mean change in FVC-% at 3, 6, 9, 12, 15 and 18 months were assumed to follow a multivariate normal distribution, with equivalent variances in the two treatment groups.
- 2) In the same manner, data from the II study was used to inform the estimated impact of prior therapy with MMF, occurring prior to randomization, on the expected mean change in FVC-% and the variance of the FVC-% values at different times after randomization.
- 3) We measured the correlation structure over time for repeated measurement of the FVC-% in individual subjects participating in the SLS I study and applied that to the prediction of outcomes for SLS III. As one might assume, correlation between measurements taken at closer intervals is greater than measurements taken farther apart and from SLS I data the correlations among outcomes 3 months apart was 0.866, 6 months apart was 0.834, and 9 months apart was 0.802.
- 4) Treatment with cytotoxic therapy (MMF or CYC) is associated with an initial period of deteriorating lung function during the first 3-6 months of treatment that appears due to the required titration of cytotoxic medication over several months and the relatively slow clearing of existing immune mediators that drive inflammation and tissue destruction. This initial loss of lung function can average from -0.25% to -2.5%.
- 5) After an initial 3-6 month period that is associated with a relative decline of lung function, continued treatment with cytotoxic therapy is associated with a relative improvement in lung function over time that ranges from approximately +2.0 to +3.0% at 12 months and from approximately +3.0 to +5.0% at 18 months.

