#### Screening criteria that met prior to moving forward to HRCT imaging

1. Age >18 years
2. Scleroderma as determined by the 2013 ACR/EULAR classification criteria.
3. Grade  $\geq 2$  on the Magnitude of Task component of the Mahler Modified Dyspnea Index (Becomes short of breath with moderate or average tasks such as walking up a gradual hill, climbing less than three flights of stairs, or carrying a light load on the level).

4. FVC-% of  $\leq 85\%$  at screening. (The original cutpoint was  $<80\%$ ; the cutpoint was changed in protocol amendment version 1.2 [December 1, 2021] to  $\leq 85\%$ .)
5. Onset of the first non-Raynaud manifestation of SSc within the prior 84 months.

Screening HRCT imaging

6. Presence of any ground glass opacification (any GGO) on thoracic HRCT

Final screening criteria fulfilled at Baseline Visit, but prior to randomization

7. Repeat FVC-% at the baseline visit within 10% of the FVC-% value measured at screening. If these criteria are not met, a repeat FVC-% may be obtained within 7 days and the subject may qualify for randomization if the repeat FVC-% agrees within 10% of the FVC-% obtained at screening.

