## 10.2 Secondary Efficacy Analyses

### 10.2.1 Secondary Analyses of Primary Efficacy Endpoint

Several sensitivity analyses are performed to assess how alternative approaches to missing data and model assumptions affect the conclusions of the analysis of the primary outcome:

1. Analysis of the primary efficacy variable as described in section 10.1 is performed using the PP population.
2. Analysis of the primary efficacy variable described in section 10.1 with the m-ITT analysis set except that HRCT fibrosis scores in the lobe of maximal involvement (QLF-LM) at screening is added as a covariate.
3. Analysis of the primary efficacy variable described in section 10.1 with the m-ITT analysis set except that baseline mRSS is added as a covariate.
4. Analysis of covariance (ANCOVA) is used to analyze the change of FVC-% from baseline to month 18 (that is, FVC-% at month 18 - FVC-% at baseline). The model includes the treatment group, baseline FVC-% and prior MMF therapy.
5. In addition to the assessment of the overall trajectory of pulmonary response which integrates the timing of the onset of response and the overall magnitude of effect at 18 months, we evaluate the individual components of this response. This is accomplished by using the linear mixed effects model with same covariates described for the analysis of primary efficacy variable and provide adjusted estimates of change from baseline in FVC-% for each treatment group and treatment difference for each time point (e.g., 3, 6, 9, 12, 15 and 18 months).
6. Descriptive statistics are provided to assess more granular changes in FVC-% by treatment adherence (e.g., premature discontinuation of study treatment prior to 3, 6, 9, 12, 15 and 18 months) in the completers population.

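### The FVC-% models adjust for the baseline-visit test alone and leave the screening test unused, which costs precision in level comparisons but not in the treatment-by-month slope

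*SAP*

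**What the plan says.** **Tests available.** Protocol 7.1.1.1 states: "Spirometry measurements will be performed at entry (screening), just prior to initiation of study medication (baseline) and every 3 months". Screening Visit 1 falls "preferably within 60 d, but no earlier than 90 d prior to randomization" (Protocol 7.2.1.1). A substitute test up to 30 days older is accepted if it was done at the same facility and passes the Pulmonary Function Core's review. Entry also requires, in SAP 6.2.1 criterion 7, "Repeat FVC-% at the baseline visit within 10% of the FVC-% value measured at screening". Every eligible participant should therefore have two FVC-% values before randomisation. A note to Protocol 5.1.4 adds: "Inter-test variability for FVC-% can range up to 10" per cent.

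**Values used.** The SAP 10.1 model is fitted "with terms for baseline FVC-%, treatment group, month, the interaction of month and treatment group, and prior MMF therapy". For the month-18 ANCOVA, SAP 10.2.1 item 4 says: "The model includes the treatment group, baseline FVC-% and prior MMF therapy". Screening FVC-% serves eligibility and enters no model. A screening covariate is not foreign to the plan, because SAP 10.2.1 item 2 adds screening QLF-LM.

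**Contrast tested.** SAP 10.1 says interest lies in mu3, the treatment-by-month term. It then describes an F-test of mean change over the treatment period, and its results table labels that quantity a slope.

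**The concern.** Test error in the one baseline value enters all six of a participant's change scores with the same sign, so averaging over visits does not remove it. Adjusting for that same noisy value removes part of it. A second pre-randomisation test removes more.

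Enrolment stopped early (SAP 14), and the model in SAP 10.1 is indexed to 51 participants against 150 planned. At that size, precision available from data already collected is worth having. What is at stake is the width of the confidence intervals for level comparisons, not their validity.

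**Working it through.** **1. The plan's own power figures.** SAP Table 7.1 gives, for 75/70/65 per arm, 82.3/78.6/76.3% (Scenario 1) and 95.6/92.6/91.8% (Scenario 2). Simulation with the stated differences, SDs, correlations, dropout and compound-symmetry fit gives 82.8/79.1/75.1% and 94.9/94.1/91.6% for the 5-df treatment-by-month F-test, all within 2 points. The month-averaged test gives only 56.9% and 78.6% at 75 per arm. The published power therefore fits the interaction test, which matters for where the gain lands.

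**2. Inputs for the screening covariate.**
- Protocol 10.5.2 item 3: "from SLS I data the correlations among outcomes 3 months apart was 0.866, 6 months apart was 0.834, and 9 months apart was 0.802". SAP Table 7.1 adds 0.790 at 12 months and 0.780 at 15 months.
- Assumed: 0.77 at 18 months, 0.76 at 21 months, linear interpolation between lags, and a 2-month gap from screening to baseline.
- Assumed: the screening-baseline correlation ρ, because the documents give nothing below 3 months. Extending the 3-to-6-month trend back to 2 months gives 0.866 + (0.866 − 0.834)/3 = 0.877. The range tried is 0.866 to 0.96.
- FVC-% levels have a common variance, set to 1. The percentage cuts do not depend on it.

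**3. Formula.** Let V be the variance of the outcome, b its correlation-scale covariance with baseline, and s that with screening. Residual variance given baseline is V − b². Adding screening removes a further (s − ρb)²/(1 − ρ²).

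**4. Six-visit mean.**
- V = [6 + 2(5×0.866 + 4×0.834 + 3×0.802 + 2×0.790 + 0.780)]/36 = 30.864/36 = 0.8573
- b = (0.866 + 0.834 + 0.802 + 0.790 + 0.780 + 0.77)/6 = 0.8070
- s, at lags 5, 8, 11, 14, 17 and 20 months, = (0.8447 + 0.8127 + 0.7940 + 0.7833 + 0.7733 + 0.7633)/6 = 0.7952
- V − b² = 0.8573 − 0.6512 = 0.2061
- At ρ = 0.877: (0.7952 − 0.7077)²/0.2309 = 0.0331, and 0.0331/0.2061 = 16.1%

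**5. Month 18.** V − b² = 1 − 0.77² = 0.4071, with s = 0.7633. At ρ = 0.877: (0.7633 − 0.6753)²/0.2309 = 0.0336, which is 8.2%.

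**6. Linear slope over months.** A baseline error common to all six changes cancels from a slope, so b and s are close to zero (−0.0062 and −0.0051 against V = 0.00185).

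| ρ | Six-visit mean | Month 18 | Slope |
|---|---|---|---|
| 0.866 | 18.0% | 9.2% | <0.1% |
| 0.877 | 16.1% | 8.2% | <0.1% |
| 0.90 | 12.1% | 6.4% | 0.1% |
| 0.96 | 2.6% | 1.8% | about 0.5% |

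**7. Scale.** In participants, 51 × [1/(1 − cut) − 1] gives about 10 at ρ = 0.877, 7 at 0.90 and 1 at 0.96.

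For power, two-sided at 0.05 as in SAP 8.6, take 51 participants, the planned dropout, a level SD of 9.35 (assumed) and correlations extrapolated to the 2-month gap. The mean-change test goes from 31.9% to 36.6% (Scenario 1) and from 49.0% to 55.7% (Scenario 2). Scenario 1 power for linear mu3 stays at 17.6%.

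**8. Entry rules.** The steps above ignore selection. A simulation of 51 participants with complete data, level SD 8-10, entry selection and the 10-point agreement rule gave cuts of 11-14% (mean) and about 5% (month 18). Without selection, that set-up gave 16-19% and 8.5-9%.

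**The case against.** **The named parameter does not benefit.** SAP 10.1 points to mu3, and the published power fits an interaction test. A reader might infer that the primary treatment comparison is inflated by baseline error. For mu3 the documents do not support that, because the error cancels. This part of the objection stands in full. It does not reach the mean-change F-test and monthly confidence intervals of SAP 10.1, the visit-specific differences of 10.2.1 item 5 or the ANCOVA of item 4.

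**The size rests on an undocumented correlation.** This also stands. A reader might take one figure, such as 11-14% of variance or 5-6 points of power, as the gain. The documents fix no such number. SAP Table 7.1 heads its correlations AR1, and under a true AR(1) process screening would add nothing once baseline is known. The listed values are not AR(1), since 0.866² = 0.750 against 0.834, so the gain depends on that slow decay being real. Nor does one level SD fit the plan's change SDs: SD/√[2(1 − r)] runs from 7.9 at 3 months to 10.6 at 12 months. That affects the power figures and leaves the percentage cuts in the table unchanged.

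**The two tests may differ for real reasons.** Up to 90 days can pass, or 120 with a substitute test, and an MMF washout or prednisone reduction may fall in between. This is fair. The screening value can still predict later FVC-%, but it is not a pure repeat of the baseline test.

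**The planned model is legitimate.** Change from baseline with baseline as covariate is unbiased under randomisation and already removes part of the error. At level SD 9.35, the SD of the six-visit mean falls from 4.61 (unadjusted change) to 4.24 (baseline) and 3.89 (both). A reader might infer bias, and nothing in the documents supports that.

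**Conclusion.** The point holds as a low-cost gain in precision for level comparisons. With complete data and no entry selection, the cut in variance of the six-visit mean difference is about 16-18% at a screening-baseline correlation of 0.866-0.877, 12% at 0.90 and 3% at 0.96. The month-18 cut is about 8-9%, falling to 2%. Entry selection lowers these figures. For mu3 the gain is about 0.5% or less.

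The conclusion rests on applying the plan's lag correlations to FVC-% levels, extrapolating beyond 15 months, and assuming the screening-baseline correlation. Whether the primary test benefits depends on a choice that SAP 10.1 leaves open: it does if the test is mean change, and it does not if the test is mu3.

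**What to change.** Before unblinding:

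1. State in SAP 10.1 whether the primary test is mean change over the treatment period or mu3.
2. Add screening FVC-% as a fixed covariate in SAP 10.1, in 10.2.1 item 5 and in the month-18 ANCOVA of 10.2.1 item 4. Define it as the Screening Visit 1 test, or the accepted substitute, from the screening that led to randomisation, since SAP 6.4.1 also lists rescreening visits.
3. Recalculate it with fractional age, because SAP 6.4.1 rounds age down at screening for eligibility.
4. State which value is baseline when the baseline test was repeated within 7 days.

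Matching screening covariates for FVC (ml) and DLCOHb-% in 10.2.2 item 1 are optional, as no size of gain was computed for them.

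The cost is one degree of freedom per model, a short SAP amendment and an entry in SAP 14, because Protocol 10.4.2 specifies the model without this term. No new data are needed. SAP 8.1 describes the SAP as finalised before lock and unblinding. If the data are already unblinded, keep the planned model and report the extra covariate only as a labelled sensitivity analysis.
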